3. STUDY DESIGN

The Behavioral Economic Applications to Geriatrics Leveraging Electronic Health Records (BEAGLE) trial is a single site, cluster-randomized controlled trial with practice as the unit of randomization. The primary aim is to test the ability of an intervention based on behavioral economic principles to reduce the

rates of commonly occurring inappropriate testing and treatment in geriatric patients across 3 domains: PSA, UA/UC, and DM. We will randomize practices using a 1:1 allocation; clinicians at intervention practices will receive the intervention when an eligible patient is seen. If physicians at intervention clinics wish to override the clinical decision support tool, they will need to provide justification that appears in the patient's EHR (accountable justification). Clinicians at control practices will receive a one-time education module about the risks of over-treatment and testing in these areas.

We will enroll approximately 350 clinicians from 60 participating primary care clinic sites and collect baseline data for the 12 months leading up to the intervention start (monthly data collected using a look-back window of 12 months). All clinicians will receive a one-time education module about the risks of over-treatment and testing in these areas at the time of consent and enrollment. Clinician surveys will be administered at the time of enrollment and after the intervention is completed. The 3 co-primary outcomes are quality measures [detailed below in section 6]. Secondary outcomes are patient safety measures [detailed below in section 6]. The 18-month intervention period will be followed by a 12-month follow-up period to measure persistence of effects after interventions end. Patient-level data from EHRs at participating practices were abstracted at 3 points [detailed below in section 11].

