10. STATISTICAL CONSIDERATIONS

10.1 General Design Overview

Hypotheses

Our primary hypothesis is that practices randomized to receive behavioral economic interventions will have decreases over time in the over-screening, over-treatment, and over-testing of older patients who

may no longer warrant such care. This hypothesis will be evaluated in an intention-to-treat difference-in-differences framework using a mixed-effects logistic regression model. Fixed effects will include the effects of interventions over time (i.e., interactions between randomization assignment and time), using a historical period 12 months prior to the intervention period. Providers and randomization unit (clinic) will be modeled as random effects.

Design

We will conduct a cluster randomized trial using data abstracted from the EHR at one academic health system. We chose a cluster-randomized design at the clinic level to minimize spillover effects – contamination that might occur if individual providers in close proximity are randomized to different interventions. The study design for BEAGLE included the implementation of a modified constrained randomization scheme, to ensure that clinics in each study arm were similar prior to activation of the intervention.

Outcome measures

This study has 3 co-primary outcomes, referred to as PSA, UA/UC, and DM (defined in Section 6 above, and further detailed in Section 10.4 below). They capture the over-testing, over-screening, and over-treatment of older patients, whose medical needs may have evolved to require less care.

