10.2 Sample Size and Randomization

Power Calculations

Study power for BEAGLE was designed around estimating minimum detectable absolute rate reductions for the three co-primary outcome measures at the individual level. Power calculations were done for a 2-level mixed effects logistic regression model that included a random intercept for clinic using PASS software. Historic data, from a period spanning X, 2017 – Y, 2018 were used to estimate an inter-clinic correlation coefficient of 0.017. In all calculations, we assumed a two-sided type I error of 5% (Bonferroni-corrected to $0.05/3 = 0.017$), 80% power, 30 clinics in each arm, and that patients would be divided equally between clinics in 2 groups. Initial calculations assumed baseline event rates and sample sizes described in Table 1. These analyses should have been conservative, as our assumed sample size was derived from an historic 12-month period, while the study follow-up period was 18 months. We did not assume any clinic drop-out, as all data will be available via the EHR. With these assumptions, we anticipated having adequate power to detect an absolute difference of roughly 4% for each of the measures. For the PSA and UA/UC outcomes, this corresponded to a relative risk between 0.80 and 0.87; for the DM outcome, it corresponded to a relative risk between 0.73 and 0.81.

Table 1. Summary of power calculations for the BEAGLE study.

	PSA N=9,500			DM N = 6,600			UA/UC N = 15,000		
	20%	25%	30%	15%	20%	25%	20%	25%	30%
Baseline event rate	20%	25%	30%	15%	20%	25%	20%	25%	30%
Minimum detectable absolute rate reduction	4.1%	4.5%	4.8%	3.9%	4.4%	4.8%	3.8%	4.2%	4.4%
Corresponding relative risk	0.80	0.82	0.84	0.74	0.78	0.81	0.81	0.83	0.85

Treatment Assignment Procedures – Constrained Randomization

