10.5 Statistical Analyses

We will use the following descriptive statistics to characterize the sample: Means and medians for continuous measures, frequencies for count data, standard deviations and interquartile ranges for variance.

To test our 3 co-primary hypotheses, we will employ a mixed-effects hierarchical logistic regression model to estimate the adjusted marginal effect over time of each intervention on the 3 co-primary outcomes. Fixed effects will include intervention assignment, time period (historical baseline versus intervention period), time period interacted with intervention assignment, time (continuous, linear), and a 3-way interaction term between time period, intervention, and time (continuous). The coefficient on the 3-way interaction term will represent whether the log-odds of the monthly rate of change in each co-primary outcome differs between intervention and control patients during the intervention period. Providers will be included as random effects. To isolate the effect of the intervention on the co-primary outcomes, we will also include fixed effects for the variables included in the constrained randomization procedure.

The secondary and safety outcomes will be examined in a similar fashion. If they are sufficiently rare (for example, no events in a given month), model convergence may become an issue. First, we plan to expand the time frame from months to quarters and fit the same model. If that fails, we will abandon the time-varying aspect of the analysis and do one pull for the historical baseline period and one pull for the intervention period. The mixed effects logistic regression model would then be run without including continuous time. If that still fails to converge, we will exclude the random effects for providers and use a fixed effects logistic regression model.

Last, the three co-primary outcomes of interest will be examined in the following pre-specified subgroups:

- Sex (DM measures only)
- Race and ethnicity
- Age groups (for UA/UC: 65-74, 75-84, 85+) (for PSA: 76-79, 80-84, 85+) (for DM: 75-79, 80-84, 85+). We will also examine for effects on patients younger than the target populations (for UA/UC: 50-64, PSA: 70-75, DM 65-74).

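### The last fallback for non-converging secondary and safety outcomes makes no allowance for clustering in a clinic-randomized trial, so its standard errors are not assured to be valid.

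*Combined protocol and SAP*

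**What the plan says.** Section 3 describes a "single site, cluster-randomized controlled trial with practice as the unit of randomization". Section 10.1 states the model for the primary hypothesis as a difference-in-differences: "Providers and randomization unit (clinic) will be modeled as random effects". Section 10.5 lists fewer random effects: "Providers will be included as random effects". It names no clinic term there.

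For the other outcomes, section 10.5 says: "The secondary and safety outcomes will be examined in a similar fashion". It then foresees trouble: "If they are sufficiently rare (for example, no events in a given month), model convergence may become an issue". The remedies come in order:

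1. Move from months to quarters.
2. Drop continuous time and "do one pull for the historical baseline period and one pull for the intervention period".
3. If that also fails, "we will exclude the random effects for providers and use a fixed effects logistic regression model".

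Section 10.5 also puts the constrained-randomization variables into its model as fixed effects. Section 10.2 shows that these are eight descriptors of each clinic, not indicators for the clinics. No robust standard error, GEE, permutation test or clinic-level analysis is named anywhere in the chain.

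**The concern.** After the third step no random effect is left, and patients of the same clinic and clinician are treated as independent. The plan's own power calculation in section 10.2 does not treat them so: it uses an "inter-clinic correlation coefficient of 0.017".

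The chain covers the three safety endpoints that sections 8 and 10.4.2 class as serious adverse events: emergency or hospital care for possible UTI or sepsis, the same for hyperglycemia, and poor glucose control after tight control. A standard error that is too small could produce a false signal of harm or benefit on one of these. One that is too large could hide a real harm.

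**Working it through.** **Inputs from the documents.** 60 clinics, 30 per arm; ICC 0.017; co-primary sample sizes 6,600 (DM), 9,500 (PSA) and 15,000 (UA/UC), all from section 10.2. Dividing by 60 gives m = 110, 158 and 250 patients per clinic. These sizes are borrowed, because none are given for secondary or safety outcomes. The documents state no figure for the fallback model, so there is none to reproduce.

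**Assumed.** Event rates, the stability of clinic effects between periods, and patient overlap between the two pulls.

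**Step 1: which contrast is tested.** The second step keeps a baseline pull and an intervention pull, and the third step removes only the provider effects. The tested term is therefore arm by period. A clinic effect that is the same in both periods largely cancels from it.

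**Step 2: formula on the ICC scale.** Let CAC be the correlation of a clinic's effect between periods. With different patients in the two pulls, the ratio of true to naive variance is about 1 + (m − 1) × ICC × (1 − CAC). The true size of a nominal 5% test is 2{1 − Φ(1.96/√ratio)}.

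- CAC = 1: ratio 1, size 5%.
- ICC 0.017, CAC 0.8: 1 + 109 × 0.017 × 0.2 = 1.37 (m = 110) and 1 + 249 × 0.017 × 0.2 = 1.85 (m = 250). Sizes 9% and 15%.
- ICC 0.017, CAC 0.5: ratios 1.93 and 3.12, sizes 16% and 27%.
- ICC 0.001 to 0.005, CAC 0.5 to 0.8: sizes 5% to 12%.

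**Step 3: the same on the logit scale, for rare events.** A clinic-by-period standard deviation s on the logit scale corresponds to about p(1 − p)s² on the ICC scale, where p is the event rate. The variance ratio is then about 1 + (m − 1) × p(1 − p) × s². With s = 0.3 (s² = 0.09):

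| Event rate | m | Variance ratio | True/naive SE | Size |
|---|---|---|---|---|
| 0.5% | 110 | 1 + 109 × 0.004975 × 0.09 = 1.05 | 1.02 | 6% |
| 0.5% | 250 | 1.11 | 1.05 | 6% |
| 2% | 110 | 1 + 109 × 0.0196 × 0.09 = 1.19 | 1.09 | 7% |
| 2% | 250 | 1.44 | 1.20 | 10% |
| 5% | 110 | 1 + 109 × 0.0475 × 0.09 = 1.47 | 1.21 | 11% |
| 5% | 250 | 1 + 249 × 0.0475 × 0.09 = 2.06 | 1.44 | 17% |

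Simulation of the unclustered arm-by-period test, with 60 clinics and s from 0 to 0.3, agrees: about 5-7% at 0.5%, 5-11% at 2% and 4-19% at 5%. When clinician-level shifts were added (assumed standard deviations 0.2 to 0.4, with clinic shifts of 0.15 to 0.3), size was 4-7% at event rates of 0.2-0.5%, 6-15% at 2%, and 9-41% at 10-20%.

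**Step 4: the same patients in both pulls.** Positive correlation within a patient reduces the true variance of a change. If overlap times within-patient correlation is 0.1 to 0.3 (assumed) and clinic effects are stable, the true/naive ratio is √0.9 = 0.95 to √0.7 = 0.84. The naive standard error is then too large.

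**Step 5: does the remedy hold its size?** Clinic-clustered errors in the same kind of simulation gave about 4-7%.

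**The case against.** The strongest defense is that this is a third, conditional step. It does not govern the co-primary outcomes, and it is reached because an outcome is rare, which is where clustering matters least. At event rates of 0.5% or less the simulated size stays at 4-7%. The retained clinic descriptors may also absorb some between-clinic variation. All of this stands, and it is why the point is minor. It does not close the gap. The trigger is non-convergence, with no ceiling on the event rate, and clinic descriptors do not make patients within a clinic independent.

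Three stronger readings are tempting but not supported.

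- *The standard errors must be too small, by the usual design effect.* A reader might compute 1 + (m − 1) × 0.017 = 2.85, 3.67 and 5.23, and so sizes of 25%, 31% and 39%. That arithmetic is correct for a comparison of arms in a single period, which the fallback does not make. An ICC of 0.017 is also a poor guide here. On the approximation in step 3, at a 0.5% event rate it implies a clinic standard deviation of √(0.017/0.004975) = 1.85 on the logit scale, against √(0.017/0.16) = 0.33 at 20%.
- *Repeated records per patient make it worse.* By this step the monthly records have been replaced by two pulls. A patient in both pulls pushes the error the other way, as step 4 shows. Several records per patient within one pull could inflate it, but the plan does not describe that.
- *A fixed effects model means an indicator for every clinic or clinician.* The text does not say so. With about 350 clinicians and rare events it would be impractical, and it would remove only the stable part of the clustering.

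The mismatch between sections 10.1 and 10.5 over the clinic effect concerns the main model. It needs its own resolution and adds no weight here.

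**Conclusion.** The gap is real: as written, the last step gives no assurance of a valid interval or p-value in a trial that randomized clinics. The direction of the error is not fixed, because it depends on whether clinic effects move between periods and on how many patients appear in both.

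The plan gives some reason to expect movement. Section 5.3 reports that the pandemic severely disrupted primary care and that March to August 2020 is excluded, so the interruption falls between the two periods. Section 10.2 notes that six practices joined the system during the baseline year.

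Under the assumptions shown (clinic-by-period standard deviation up to 0.3, co-primary clinic sizes, no patient overlap), the true size of a 5% test ranges from close to nominal for very rare outcomes to 19% at a 5% event rate with the largest clinics. The documents cannot narrow this range. This is a cheap improvement, not a threat to the trial's main conclusions.

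**What to change.** Replace the final sentence of the fallback chain in section 10.5 with one that keeps the simpler logistic model, states that the arm-by-period term is the effect tested, and bases inference on clinic-clustered standard errors with a small-sample correction. Clustering at the clinic also covers clinicians within a clinic and patients who appear in both pulls at the same clinic. With 60 clinics this is feasible and needs no random effect to converge.

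An alternative is to compare the arms on the 60 clinic-level changes in event proportion from baseline. The changes must be used: comparing intervention-period proportions alone would discard the baseline and alter the effect being estimated.

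The cost is one sentence and intervals that may be somewhat wider.

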11. DATA COLLECTION AND QUALITY ASSURANCE

11.1 Data Collection Forms

Two types of data were collected: 1) data from electronic medical and billing records, abstracted from Northwestern Medicine's Electronic Data Warehouse; and 2) data from online surveys at the beginning and end of the study.

11.2 Data Management

The study analyst, [name], extracted data from the NMEDW at 3 points: end of baseline period, end of intervention period, and end of additional follow-up period.

Both the baseline and 18M surveys will be administered via REDCap.

11.3 Quality Assurance

Extensive quality assurance was conducted during the pilot R21 phase of this study.

12. PARTICIPANT RIGHTS AND CONFIDENTIALITY

12.1 Institutional Review Board (IRB) Review

The study protocol and the informed consent document will be reviewed and approved by the Northwestern University Institutional Review Board (IRB).

12.2 Consent Process

Not applicable. We were granted a waiver of consent for clinician and patient record review. Here, we provide details about the alteration of the consent process for our online consent script ahead of baseline and study close-out clinician surveys.

12.2.1 Patient Consent Process

We were granted a waiver of the consent process to review (NMEDW query) patient medical records to collect study data because we met the following criteria:

- This research was NOT FDA-regulated and only involved adults
- The research involved no more than minimal risks to subjects. Review of medical record data had strict inclusion and exclusion criteria and identified data was only seen by the study analyst extracting data from EDW.
- This research could not practically be carried out without the waiver. We were attempting to describe clinician testing and treatment behavior across the entire geriatric patient population and to use these measures as the basis for clinician interventions that turn on and off based on data that reside within the EHR.
- To understand how the nudges work, we must have access to identified patient and clinician data. Our analyst assigned a study identifier and stripped out all identifiers prior to finalizing and sharing the study analytic files.
- The waiver will NOT adversely affect the rights and welfare of subjects.
- Subjects (patients) will not be provided any study information as they will be unaware of study participation.

12.2.2 Clinician Consent Process

We were also granted a waiver of consent for clinician record review because we met the following criteria:

- This research is not FDA-regulated. It is a quality improvement study designed to evaluate clinical decision supports impact on guideline recommended care. Clinicians' actions are in no way restricted.
- The research does not involve non-viable neonates. Adult NM clinicians will be presented alerts in the EHR when criteria within the chart are met.
- The research involves no more than minimal risk. Clinical decision supports are intended to help clinicians make safer clinical decisions for their patients. Their interactions with study nudges and their performance on study quality measures will have no effect on their NM employment. Performance data will be confidential.
- The waiver of consent will not adversely affect the rights and welfare of clinicians who interact with study nudges. Clinicians have choices in how they respond to nudges. Clinicians will be able to order tests and treatments in the exact same way as prior to the initiation of this pilot study.
- The research could not practically be carried out without the waiver of consent. This study attempts to describe clinician interactions with EHR tools intended to improve quality of care. If we consented clinicians for this study, clinicians that would volunteer to participate would very likely be different from non-volunteering clinicians. *The goal of the study is to develop and test clinical decision supports that could be turned on for large populations of clinicians and not just the subgroup of clinicians that may be interested.*
- We will inform all participating clinicians about study nudges, will respond promptly to any questions or concerns they have about their experience interacting with them, and will provide summary quality measure data at the clinic level at the end of the study.

Further, we were granted a waiver of documentation of consent for the clinician surveys administered at baseline and end of the intervention. We used REDCap functionality to present IRB approved informed consent language as first section of survey and require a 'yes' response in order to proceed and view/interact with online survey. If a clinician refused participation by marking 'no' to consent item, they will only see a 'thank you, please close your browser' message and we no longer sent reminders to that clinician. Clinicians were instructed they can print the consent language from their browser if they would like a hard copy to keep for their records. The consent language was presented as first section on both the baseline and the 18M follow-up survey.

Both the study PI ([name]) and project manager (TB) had their contact details included with the online consent script. They responded promptly to any potential participant who reaches out with questions or concerns. The full study team reviewed the online consent language to ensure it had all informed consent elements that are necessary.

PROTECTED HEALTH INFORMATION (PHI AND HIPAA)

This study involves the use of Protected Personal Health Information (PHI) accessed through NM EDW. We were granted a waiver of HIPAA authorization. We have reviewed the HIPAA Waiver of Authorization checklist (HRP-441) and provide details below.

- We clearly define here the description of the PHI our study will access and why it is necessary for this research.
- The use of PHI involves no more than minimal risk to the privacy of individuals based on the following:
 - An adequate plan is in place to protect the identifiers from improper use and disclosure. See data security section above.
 - An adequate plan is in place to destroy the identifiers at the earliest opportunity consistent with conduct of the research. We will destroy identifiers as soon as study analytic files are created and study manuscripts accepted. Identifiers will be destroyed prior to the end of the grant period.
 - Adequate written assurances that the protected health information will not be reused or disclosed to any other person or entity, except as required by law, for authorized oversight of the research study, or for other research for which the use or disclosure of protected health information for which an authorization or opportunity to agree or object is not required by 45 CFR 164.512.
- Given that the research describes the entire geriatric patient population with a visit during the study look-back or intervention period, this research could not practicably be conducted without the waiver.
- The research could not practicably be conducted without access to PHI.

12.3 Participant Confidentiality

We will only extract the minimum necessary data to answer research objectives. All analytic files will be de-identified.

Clinician surveys focus on their clinical role and attitudes and should not feel intrusive. However, clinicians can skip any survey items they wish and still submit the survey.

Clinic leaders and individual clinicians will be provided study team contact information so they can report concerns or complaints about study interventions at any time. We will also be informed of any tickets to Epic helpdesk that are related to study interventions by NM Epic programmers.

12.4 Study Discontinuation

While this was a minimal risk study, we established a DSMB. Following each DSMB meeting, the board made recommendations to the IRB as to whether the study should continue or if changes to the protocol were necessary for continuation.

